10.4 Monitoring of Subjects with Adverse Events

Each subject must be carefully monitored for AEs. After an initial SAE report the Investigator is required to follow-up proactively each subject and provide further information to the Sponsor or designee on the subject's condition. Subjects who experience the onset of an AE thought to be related to IMP or IVT injection prior to their final visit (Visit 5/EOS) will be monitored until the resolution of the AE or for 30 days after the AE occurs, whichever comes first. AEs not resolved after 30 days will be listed in the CRF as continuing/not resolved.

10.5 Other Safety Assessments

10.5.1 Clinical Laboratory, Physical Examination, Vital Signs Parameters, and ECG

For laboratory parameters, physical examination findings, vital signs, and ECG any clinically significant abnormalities that are causally related to the study medication or study procedure in the judgment of the Investigator will be recorded as AEs.

In the event of unexplained abnormal laboratory test values, the tests should be repeated immediately and monitored until the values have returned to the reference range and/or an adequate explanation of the abnormality is identified.

10.5.2 Concomitant Medications

During the study, any medication taken by the subject is to be reported by the subject. Any changes in concomitant therapy during the study will be documented, including cessation of therapy, initiation of therapy, and dose changes. The Investigator or designee will record any concomitant therapies given for the treatment of AEs on the concomitant medication page of the subject's source document and eCRF.

10.6 Procedures in Case of Pregnancy

If a subject or the partner of a male subject becomes pregnant during the study, the subject should inform the Investigator and provide a copy of the positive pregnancy test and estimated date of the pregnancy. Pregnancy in itself is not regarded as an AE unless there is a suspicion that the IMP may have interfered with the effectiveness of a contraceptive medication.

The outcome of all pregnancies (i.e., spontaneous miscarriage, elective termination, normal birth, or congenital abnormality) that begin before Visit 5 must be followed up and documented even if the subject was discontinued from the study. A pregnancy outcome of a congenital abnormality/birth defect or of a spontaneous miscarriage would qualify as an SAE and be reported to the Sponsor or designee for processing to the regulatory authorities. A pregnancy outcome of an elective abortion without evidence of complications would not be processed as an AE.

11. STATISTICAL ANALYSIS

Database lock, statistical programming and analysis, and reporting will be performed by the CRO.

11.1 Data Collection, Database Lock, and Coding of Terms

Electronic CRF/electronic data capture will be used for data collection during the long-term follow-up study and a Data Management Plan will be prepared by the CRO, PRA Health Sciences, detailing the procedures leading to database lock. Assessment data from the RESCUE/REVERSE clinical database that is needed to complete the statistical summaries and analyses that are required for this long-term follow-up study will be imported into the GS-LHON-CLIN-06 clinical database. When the GS-LHON-CLIN-06 clinical database has been found to be complete and accurate, the database will be locked. Any changes to the database after that time can only be made by written agreement between GenSight Biologics and PRA.

Coexistent diseases and AEs will be coded using the current version of MedDRA. Previous and concomitant medications will be coded using the latest available World Health Organization (WHO) Drug Reference Dictionary.

11.2 Statistical Analysis Plan

A statistical analysis plan (SAP) will be prepared after the protocol is approved and before database lock occurs. The SAP will provide further details regarding the endpoints, data handling rules, and the statistical methods to be used to address all study objectives and endpoints. The SAP will also include display formats for the summary and analysis tables, listings, and graphical displays.

Data for quantitative variables will be presented by arithmetic mean (for other continuous variables), standard deviation (SD) median, first quartile (Q1), third quartile (Q3), minimum and maximum. Data for categorical and binary variables (responder analysis) will be presented by counts and percentages. Least square means, 95% confidence interval (CI) and P-values will be reported derived from models and statistical tests.

11.3 Sample Size Estimation

A formal sample size calculation will not be performed because this is an extension study and no inferential or formal statistics of the primary endpoint of the study will be conducted. The study population is limited to the number of subjects treated in the RESCUE and REVERSE studies.

11.4 Analysis Populations

11.4.1 Safety Population

The safety population will be defined as all subjects who received study medication in RESCUE or REVERSE Phase III studies and consented to be enrolled in this long-term follow-up study. This population will be used as the population for all safety analyses.

11.4.2 Intent-to-treat Population

The intent-to-treat population will be defined as all subjects who received study medication in RESCUE or REVERSE Phase III studies and consented to be enrolled in this long-term follow-up study. This population will be used as the population for efficacy and QOL analyses. This

population is identical to the safety population.

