According to the EMA Committee for Medicinal Products for Human Use Guideline, entitled “Follow-Up of Patients Administered with Gene Therapy Medicinal Products,” and the United States Food and Drug Administration (US FDA) Center for Biologics Evaluation and Research Guidance for Industry (2006) entitled, “Gene Therapy Clinical Trials: Observing Subjects for Delayed Adverse Events,” viral vectors without integration, latency, or reactivation potential like AAV vectors present a low risk for gene therapy-related delayed adverse reactions. Although the FDA indicated that long-term follow-up is not considered necessary for this clinical development program, the EMA recommends a yearly monitoring plan up to 5 years post-treatment.

The regulatory intention of further observation is to determine the sustainability of efficacy, or whether declining efficacy after administration of gene therapy IMP occurs or whether more time is needed for tissue to be fully functional. For safety, the intention is to determine delayed-onset of adverse events (AEs), and to determine any additional unexplored long-term risks. The EMA refers to the Guideline (2008) entitled “Safety and Efficacy Follow-up: Risk Management of Advanced Therapy Medicinal Products” for possible delayed risks. One area for long-term observation is the potential risk directly related to the administration procedure of advanced therapies, and for this program would be the technique of IVT injection and any associated long-term effects.

In summary, all treated subjects in the RESCUE and REVERSE studies will be offered participation in the GS-LHON-CLIN06 study for the purpose of long-term safety evaluations, but only those providing informed consent and meeting eligibility criteria will be included in the study.

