7. INVESTIGATIONAL PLAN

7.1 Overall Study Design and Plan

This study will be a multinational multicenter prospective non-interventional long-term follow-up clinical study of subjects previously treated with GS010 in either the RESCUE or REVERSE studies. Of the 7 investigational centers participating, 4 are located in Europe (1 each in France, Germany, Italy, and the United Kingdom,) and 3 are located in the United States.

[figure not shown]
Subjects will be enrolled in the long-term follow-up study when informed consent is provided and inclusion/exclusion criteria are met. Enrollment will occur during the Inclusion Period, which will be during the RESCUE and REVERSE study Week 96/End-of-Study (EOS) Visit or anytime up to 1 day prior to the long-term follow-up study Visit 2 (Day 180). Preferably, the assessments required to be performed during the Inclusion Period will be conducted at the RESCUE and REVERSE study Week 96/EOS visit; however, if the subject cannot undergo all assessments at that time, the assessments may be performed at a later date during the Inclusion Period, but no later than one day before the Year 2.5 visit (Day 180).

The study population will be limited to the number of subjects treated in the RESCUE and REVERSE studies. The total length of the long-term follow-up study will be 3 years and the total length of the subject follow-up from IMP administration will be 5 years. The RESCUE and REVERSE long-term follow-up study is planned to start towards the end of 2017 and study start will be defined as the first subject's first visit in this study. The approximate study end date is planned to be towards the end of year 2022 after the last subject's last visit.

The follow-up will include onsite assessments of safety, QOL, and efficacy as in the RESCUE and REVERSE studies. The study will include 5 follow-up study visits: at 2.0-, 2.5-, 3-, 4-, and 5 years post-treatment.

Statistical analysis of the data will include descriptive summaries of safety, QOL assessments, and statistical testing of efficacy endpoints.

Figure 1: Study Design Schematic of the Long-term Follow-up of Subjects from the RESCUE and REVERSE Clinical Studies

Note: Inclusion into the long-term follow-up study will be allowed from W96 up to 1 day prior to Y2.5.

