7.3.2 Exclusion Criteria

If any of the following apply, the subject **MUST NOT** enter the study:

1. Subject is unwilling or unable to comply with the protocol requirements.
2. Subject has any medical or psychological condition that, in the opinion of the Investigator, may compromise their safe participation in the study.
3. Subject is taking or intending to take idebenone during the long-term follow-up study period.

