11.5.2.2 LogMAR

Analysis for European Medicines Agency

The primary analysis will be performed on the intent-to-treat (ITT) population. The change from baseline to each follow-up visit in the LogMAR acuity will be the response. The change from baseline of all-GS010 eyes will be compared to the change from baseline of all-sham eyes (intra-subject comparison) using a mixed-effects ANCOVA model using the following terms (or covariate) in the model:

- Subject and eyes of the subject as random factors
- The baseline LogMAR
- Treatment

The investigative site will not be included in this analysis as the number of subjects recruited per site will be very small. However, stratification by geographical area will be performed as a sensitivity analysis. Neighboring countries can be pooled to reach at least 9 subjects per geographical entity. The analysis will be performed based on alpha of 0.05 (two-sided test).

An additional model will add the treatment by geographical interaction to investigate lack of generalizability of the treatment effect.

Analysis for Food and Drug Administration

The primary analysis will be performed on the ITT population. The change from baseline of the best-GS010 treated eyes will be compared to the change from baseline of the best-sham eyes (inter-subject comparison) using an ANCOVA with baseline LogMAR as covariate. The analysis will be performed using an alpha of 0.05 (two-sided test). The statistical significance in favor of the best-GS010 treated eyes against the best-sham eyes will show evidence of the advantage of using GS010 for halting visual acuity loss or improving visual acuity in subjects with LHON. The difference in the mean change from baseline (adjusted mean difference) between the two treatment groups and associated 95% confidence interval will be reported.

The center will not be included in the analysis as the number of subjects recruited per site will be very small. However, stratification by geographical area will be performed as a sensitivity analysis. Neighboring countries can be pooled together to reach at least 9 subjects per geographical entity. The pooling of countries will be performed during the masked review of data.

An additional model will add the treatment by geographical area interaction to test for a lack of generalizability of the treatment effect.

The same analysis will be repeated for worst-GS010 treated eyes against worst-sham eyes.

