11.5.5 Demographic and Baseline Characteristics Analysis

Demographic and baseline characteristics (age, gender, weight, height) will be summarized using descriptive statistics. Qualitative variables (gender) will be summarized using frequencies while quantitative variables (age, weight) will be summarized using mean, SD, median, Q1, Q3, minimum, and maximum.

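### The efficacy set is fixed by consent about two years after randomisation, so the between-subject best-eye and worst-eye comparisons are not intent-to-treat comparisons, and Year 2 needs a result on all treated subjects beside it

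*Protocol*

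**What the plan says.** **Who is analysed.** Protocol 11.4.2: "The intent-to-treat population will be defined as all subjects who received study medication in RESCUE or REVERSE Phase III studies and consented" to be enrolled here, and "This population will be used as the population for efficacy and QOL analyses". Section 5.3 says all treated subjects are offered entry, "but only those providing informed consent and meeting eligibility criteria will be included in the study". Under section 7.1, enrolment runs from the parent-trial Week 96 visit to the day before Visit 2. Eligibility selects further. One exclusion in 7.3.2 reads: "Subject is taking or intending to take idebenone during the long-term follow-up study period".

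The current SAP (6.2) calls the set mITT. It keeps the consent condition, adds availability of visual acuity data at Visit 2, and equates the set with the Safety Population, whose definition (6.1) has no such condition. SAP 8.8, which lists changes from the protocol, mentions the added per-protocol, paediatric and subset populations but not this one.

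**What is tested.** Protocol 11.5.2.2 and SAP 8.5.2.2 give two LogMAR analyses at each visit, including Year 2, at two-sided 0.05. The EMA analysis compares the two eyes within subjects. In the FDA analysis, the change in best-seeing GS010 eyes "will be compared to the change from baseline of the best-sham eyes (inter-subject comparison) using an ANCOVA with baseline LogMAR as covariate". Both documents say that significance favouring GS010 in this comparison is to be read as evidence of its advantage. The protocol repeats the analysis for worst-seeing eyes, and SAP 8.5.2.4 compares best-eye and worst-eye responders by logistic regression.

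**What is described.** Protocol 11.5.5: "Demographic and baseline characteristics (age, gender, weight, height) will be summarized using descriptive statistics". SAP 8.3 presents these by parent study and pooled, not by allocation. SAP 8.1 covers the disposition of enrolled subjects.

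**The concern.** Randomisation took place before injection, and SAP 3.1 describes a minimisation step to balance treatment across best-seeing and worst-seeing eyes. That balance belongs to everyone randomised. Membership of the efficacy set is settled after each subject has lived with the visual result for about two years.

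In the best-eye comparison the arms are different people: those whose better eye received GS010 and those whose better eye received sham. The comparison stays unbiased under the null if enrolment is unrelated to outcome, or related to it in the same way in both arms. No planned output compares enrolled with non-enrolled treated subjects, or shows vision-loss duration by allocation, although SAP 4.4 names that duration as a possible prognostic factor.

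Year 2 is the sharpest case. The visit precedes or coincides with the consent decision, and SAP 5.5.1 falls back on the parent Week 96 visit when no Year 2 visit exists. Week 96 acuity therefore does not depend on later consent, yet it is analysed only in those who consented and, under SAP 6.2, who also had acuity data at Year 2.5. If the arms selected differently, a difference in who continued could be read as a treatment effect.

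**Working it through.** **1. No figure to reproduce.** Protocol 11.3 and SAP 3.3 give no sample size calculation. Neither document gives the number treated, the number enrolled or an SD. The only design number is alpha = 0.05 two-sided (z = 1.960). Everything below is an illustration on assumed inputs.

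**2. Ceiling for one-arm selection.** If a fraction d of one arm is lost entirely from one tail of a normal outcome, that arm's mean moves by φ(z₁₋d)/(1 − d) SD.

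- d = 0.10: 0.1755/0.90 = 0.195 SD; at SD 0.45, 0.09 LogMAR.
- d = 0.20: 0.2800/0.80 = 0.350 SD; at SD 0.45, 0.16 LogMAR.

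**3. Partial selection, simulated.** Assumed: 38 per arm, SD of change 0.45 LogMAR, no true effect, enrolment unrelated to outcome in one arm. In the other arm, the odds of enrolling fall by a factor OR per SD of worse Week 96 change.

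| Enrolment in the affected arm | OR | Bias (LogMAR) | Rejection at 5% |
|---|---|---|---|
| 80% at the average outcome | 1 | 0.00 | 5.0% |
| 80% at the average outcome | 2 | 0.067 | 9.1% |
| 80% at the average outcome | 3 | 0.101 | 14.5% |
| 80% averaged over the arm | 2 | about 0.06 | 8% |
| 80% averaged over the arm | 3 | about 0.08 | 12% |

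With the protocol's 0.02 LogMAR per letter, 0.06/0.02 = 3 letters and 0.10/0.02 = 5 letters. With 90% enrolment averaged over the arm, bias is 0.03 to 0.045 and rejection 6% to 7%. With 70%, bias is 0.09 to 0.12 and rejection 11% to 18%. Selection is defined per SD, so bias scales with the SD and the rejection rate does not depend on it. For SD 0.30 the range 0.06 to 0.10 becomes 0.04 to 0.07; for SD 0.60 it becomes 0.08 to 0.13.

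**4. Separate simulation over selection patterns.** Two-sample t-test, 60 or 80 subjects in total, consent 70% to 90%, logistic slope 1 per SD (odds ratio e¹ = 2.7), no true best-eye effect.

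| Consent depends on | Bias (SD) | Type I error |
|---|---|---|
| nothing | about 0 | 4.2% to 5.5% |
| best-eye outcome, same way in both arms | about 0 | 4.8% to 6.0% |
| better of the two eyes, GS010 helping only the worst eye (0.5 SD) | 0.02 to 0.06 | about 5% |
| best-eye outcome in one arm only | 0.10 to 0.27 | 6.7% to 17.2% |
| best-eye outcome, opposite directions in the two arms | 0.18 to 0.51 | 12% to 51% |

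With all treated subjects kept in the test, the error was 4.4% to 6.1%, nominal within simulation error.

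**5. Would a table reveal it?** In the step 3 setting, 38 × 0.20 = 7.6, so about 8 subjects in the affected arm are not enrolled. A test of whether the enrolled versus non-enrolled difference in Week 96 change varies by arm detected the selection in 21% (OR 2) and 38% (OR 3) of runs at 80% enrolment, and in 15% and 27% at 90%.

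**6. The two SAP statements.** A subject who consents, has Year 2 acuity and then has none at Visit 2 is in the Safety Population (6.1) and outside mITT (6.2). The sets coincide only if no such subject exists. This SAP is dated 30 June 2022. With last visits planned for late 2022, Visit 2 should have been complete about 2.5 years earlier, in mid-2020. The statement may therefore report a fact, but no count is given.

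**The case against.** Any extension study enrols by consent, and these documents say so openly. The primary objective is safety, and SAP 8.5.4 makes all efficacy secondary. For Years 2.5 to 5 no data from this study exist on non-enrolled subjects, so no redefinition recovers the randomised set. Every subject had GS010 in one eye, and parent allocation was masked to subjects and the follow-up team (SAP 3.1), which makes strongly arm-dependent consent less likely. The best-eye ANCOVA adjusts for baseline LogMAR, SAP 8.5.2.2 summarises LogMAR for best-GS010 and best-sham eyes, and it lists a possible check of covariate against treatment. The current SAP has already dropped the plain ITT label.

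Most of this stands and limits the point to a reporting improvement. It does not remove it. Neither document says whether masking still held when consent was given, and arm-dependent experience does not need unmasking: protocol 10.3 reports that ocular inflammation was seen in the Phase III studies, and in one arm the injected eye is the better one. The idebenone exclusion could also track visual outcome. The listed diagnostics look only within the enrolled set, at baseline LogMAR, and are optional.

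Two stronger readings are tempting. A reader might infer that the best-eye result is biased. The documents do not show that: they give no enrolment counts, and selection that is the same in both arms produces no bias under the null. A reader might also infer that the sponsor can freely reuse non-enrolled subjects' data. Protocol 8.1 obtains permission to use parent-trial data here through consent to this study, and the parent-trial consent is not among the documents.

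**Conclusion.** The point holds as a cheap improvement. The efficacy set is conditioned on consent about two years after randomisation and, in the SAP, on Year 2.5 acuity data. The between-subject best-eye and worst-eye comparisons therefore lack the guarantee of comparability that the sentence about evidence of advantage relies on. The all-eyes comparison is less exposed.

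The size is unknown. Bias of about 0.06 to 0.10 LogMAR (3 to 5 letters), with type I error of about 8% to 14%, follows only if about 80% enrol, selection acts on outcome in one arm alone with an odds ratio of 2 to 3 per SD, and the assumed 38 per arm and SD of 0.45 apply.

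A reader might also take a balanced enrolled/non-enrolled table as proof that there was no selection. With about 8 non-enrolled subjects in an arm, it would usually miss selection of this strength. Nor do the documents establish that Year 2 repeats a parent-trial test, because the parent trials' own Week 96 analysis is not described.

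**What to change.** 1. Beside the Year 2 result, report the EMA and FDA LogMAR models on all treated subjects with Week 96 data. Run them in the parent-trial database, or take them from its results, where that consent permits. This removes follow-up enrolment selection at Year 2.
2. Add one descriptive table by allocation (better eye GS010 or better eye sham) and by enrolled or not enrolled, with counts, baseline LogMAR, vision-loss duration and Week 96 change. State that the absence of a visible imbalance does not rule out selection.
3. If parent-trial consent permits, add a likelihood-based repeated-measures sensitivity analysis for Years 2.5 to 5 that includes the parent-trial visits of all treated subjects. Otherwise omit it.
4. Call the set treated and consented. Reconcile the Visit 2 condition in SAP 6.2 with its equality to the Safety Population, do not apply that condition to Year 2, and record the change in 8.8. Qualify the sentence on evidence of advantage to say that the best-eye comparison is not an intent-to-treat comparison.

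The cost is SAP wording, a few tables and a check of parent-trial consent, with no added patient procedures. The downside is a less favourable label and possibly a visible imbalance. Item 4 needs no data on non-enrolled subjects.

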11.5 Statistical Methods

11.5.1 Safety Analyses

Primary Safety Analysis

Adverse events and SAEs related to GS010 IVT injection or study procedure will be summarized in two different ways: (1) systemic AEs and SAEs related to study drug/procedure, and (2) ocular AEs and SAEs related to study drug/procedure. Systemic AE data will be summarized by all subjects. Ocular AE data will be summarized by sham eye only and GS010 eye only.

Clinically significant abnormal findings observed during physical examination, vital signs measurement, ECG recording, or laboratory values will be summarized as AEs in the AE tables if the clinically significant abnormal finding is deemed as causally related to the study medication or study procedure.

The following summaries will be produced for (1) SAEs unrelated to study drug/study procedure, (2) systemic AEs/SAEs related to study drug/procedure, and (3) ocular AEs/SAEs related to study drug/study procedure, using counts and percentage as follows:

- Overall summary of AEs/SAEs related to study drug/procedure
- AEs related to GS010 IVT injection or study procedure, including the number of events reported
- AEs/SAEs related to GS010 IVT injection or study procedure by maximum severity
- AEs/SAEs related to GS010 IVT injection or study procedure leading to study discontinuation
- SAEs related to GS010 IVT injection or study procedure
- SAEs related to GS010 IVT injection or study procedure leading to death.

Events will be coded using the MedDRA and summarized by system organ class and preferred term.

Secondary Safety Analysis

The number, type, frequency, and severity of ocular or vision-related AEs, including those with no relation or any relation to the GS010 IVT injection or study procedure will be presented in the same way that the primary endpoint of ocular AEs/SAEs related to GS010 IVT injection or study procedure.

